# Post intervention:

Follow-up interviews will be conducted post-treatment to assess changes in IPV, child maltreatment risk, and child mental health. This will also be done via zoom or in person. Fathers will be offered \$60 for post-treatment assessments and mothers \$35. These will include the same assessments of reflective functioning, emotion dysregulation, IPV, and child maltreatment risk administered at baseline. Father-child interactions will be assessed via a coded free-play interaction with the target child at baseline and post-treatment. Fathers will be recorded playing with their children with an age appropriate set of pretend play toys for 15 minutes and then during cleanup time.

# Follow-up:

6 and 12 months post-intervention, fathers and coparents will participate in follow-up interviews to assess IPV, child maltreatment risk, father engagement and parenting. Participants will complete these interviews over zoom or telephone. They will be paid \$50 and mothers \$35.

# Analytic Plan.

We will use Research Electronic Data Capture (REDCap™), a widely used secure web-based software package designed for clinical trials to collect study data.

Preliminary Analysis: A series of preliminary analyses will be conducted to: (1) characterize the sample, (2) document the internal reliability of measures, (3) check for logical consistency among related variables, (4) identify outlying values that should be considered for truncation, and (5) assess whether there are significant differences in outcomes based on study therapist. Although urn randomization procedures will be used to balance distribution of specific characteristics across treatment groups, we will explore between-group differences in urn variables and other demographics and possible moderators. Data analyses will be done independently and without

knowledge of group assignment, with the participant's group assignment anonymized to "treatment 1" or "treatment 2".

Phase I Hypotheses:

- i. Fathers randomized to F4C will have higher completion rates than those in the BIP-I or BIP-G treatment. Chi-square analysis will be used to examine between group differences in treatment completion.
- ii. Fathers will report greater working alliance and satisfaction with F4C than BIP-I or BIP-G. Analysis of variance will be used to test between group differences in working alliance and client satisfaction.
- iii. Fathers receiving F4C will evidence greater improvement in RF and emotion regulation, IPV, and child maltreatment(CM) compared with fathers receiving BIP-I or BIP-G postintervention. Mixed effects regression will be used to test for between-group differences in RF, emotion regulation, IPV, and CM representing treatment effects associated with F4C versus BIP over time. Separate IPV and CM sum scores will be created. Any instance of IPV or CM by any report (self, co-parent or current partner report on the Timeline Follow Back, child protection or arrest records) will be counted to create a sum score across reports. The Child Interactive Behavior Codes of Intrusiveness and Child Avoidance will be used as our observational measures of CM risk. Total coded RF score as measured by the PDI and self-reported emotion regulation on the DERS will be used to test impact mechanisms of F4C.
- iv. Exploratory hypothesis: Test whether improved RF and emotion regulation are associated with reduced IPV and CM consistent with the F4C mechanisms of change. We will test path models: treatment group (dummy coded F4C, BIP-I or BIP-G) to each mediator (RF, emotion regulation) to the two outcomes (IPV and CM). See Statistical Analysis section for further details.

Power Analysis: A sample of 75 with planned 63 participants with complete data will provide 80% power to detect group differences with a modest effect size of .45 (see Statistical Design and Power Section).

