# Treatment Phase.

Each treatment will be delivered weekly over 18 weeks. Male participants will meet online or be contacted via phone weekly with the RA to complete self-report assessments of IPV behaviors, father-child interactions and *substance use*. The RAs will be blind to the participants' treatment conditions. Study therapists will complete weekly session reports of session content and skill acquisitions based on completed homework.

*Fathers for Change*: F4C focuses on: 1) the fathering role to facilitate engagement, 2) RF to understand self, partner and children and emotion regulation skills to reduce IPV and child maltreatment F4C focuses on understanding of emotional experiences, how they impact thinking and behaviors related to partners, co-parents and children. F4C clients will meet individually with their F4C therapist for 50 minutes per week over 18 weeks.

**Batterer Intervention Program:** The BIP is a psychoeducational intervention that will be delivered in 50- minute individual sessions over 18 weeks. The intervention focuses on the impact of violence on victims, power and control tactics, and societal influences supporting men's violence toward women. The intervention includes didactics and experiential exercises including role plays to teach management skills. anger BIP is typically delivered in a group format, however will also be adapted to an individual Therapies will be delivered either in person or via format as part of the current study. secure/password protected zoom virtual sessions. All Yale safety protocols with regard to COVID-19 will be followed.

**Therapist Training.** Master's level clinicians will be trained to deliver the study interventions. [name] will utilize the therapist training manual, slides and videos generated from her pilot studies to train F4C therapists. She will meet weekly with F4C therapists for supervision. BIP-I and BIP-G therapists will be trained by [name] using the BIP manual and training materials modified for individual treatment delivery. BIP clinicians will meet weekly with [name] for supervision and intervention adherence.

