**Treatment Fidelity.** Each intervention session will be video recorded. Trained coders will rate 20% of sessions for fidelity and change in emotion regulation/reflective functioning during therapy sessions using the F4C/BIP Fidelity Measure and the CHANGE coding system. Tape raters for fidelity will be trained by the PI coding a set of 6 practice tapes. Fidelity feedback will be provided by Drs. [name] (F4C) and [name] (BIP) in their respective supervision sessions with study therapists to ensure fidelity and allow corrective feedback. Tape raters will be trained by [name] for the CHANGE session coding system and will be supervised by [name] at the University of Delaware and [name] at the University of Connecticut. The Change and Growth Experiences Scale (CHANGE; Hayes, Feldman, & Goldfried, 2007) is an observational coding system that assesses processes of change during psychotherapy, including factors that facilitate and inhibit therapeutic change. The CHANGE has been used to code audio and video recordings of sessions or narratives from clinical trials of trauma-focused cognitive behavioral therapy (TF-CBT) for youth (Alpert et al., 2021; Canale et al., 2021; Ready et al., 2015; Yasinski et al., 2016), prolonged exposure, written exposure therapy (WET), and cognitive processing therapy (CPT) for adult PTSD (Alpert, 2021; Alpert et al., 2020; Sloan et al., 2021), as well as cognitive-behavioral treatments for depression (Abel et al., 2016; Adler et al., 2013; Hayes, Feldman, Beevers et al., 2007; Yasinski et al., 2020) and personality disorders (Hayes & Yasinski, 2015). The CHANGE has been used to identify key predictors of treatment dropout and outcomes in each of these clinical trials.

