# Phase II Hypotheses:

**AIM 1 Hypotheses:** Children of fathers who receive F4C (n=180), relative to BIP (n=180), will: (1a) experience less family violence (FV), (1b) have more positive father-child interactions, and (1c) have lower FV-related mental health symptoms (PTSD, internalizing/externalizing) at post treatment and 6- and 12-month follow-ups. The effects of both treatments on father and coparent mental health outcomes will also be examined (1d exploratory). Hypotheses will be evaluated with the broad family of latent (growth) curve models (LGM), which estimate and compare trajectories of change for each case in the data. Group differences in changes will be tested in multiple group LGM models. Following analyses for our primary study hypotheses, we will examine whether child sex moderates child mental health outcomes between the F4C and BIP groups. Power. The planned sample size of 140 F4C and 140 BIP cases provides power of .91 to detect a small to moderate effect size (d = 0.12). The current study with 140 per group (even 126) per group assuming a conservative 30% attrition at follow-up) has sufficient power to determine small differences in changes between intervention groups on outcomes. LGM models for changes in latent rather than observed scores, for three or more waves of data, have the advantage of partialing out measurement error, and increasing the statistical power by at least 20%. See Statistical Design and Power Section for estimation method.

AIM 2 Hypotheses. Compared to BIP, more F4C fathers will show profiles of healthy change in therapeutic targets: (2a) masked coding of in-session RF/ ER (i.e., increased RF and adaptive ER, decreased maladaptive ER), and (2b) between-session self-reported RF/ ER (i.e., increased

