# **Roles and Responsibilities**

[name] and the study team will review data integrity and safety during weekly team meetings. The post graduate associate and research interns will review assessment data and bring any concerns to [name] immediately if needed or in the context of weekly study review. Drs. [name] (Fathers for change) and [name] (Batterer Intervention) will also provide weekly supervision to study therapists, where they can report any concerns or safety considerations related to study interventions. Any significant study safety concerns related to participants will result in an immediate phone call to [name] and if needed Drs. [name] and [name]. [name] will not participate in data analysis. [name] or another team member masked to participant treatment group will carry out all statistical analyses related to study intervention comparisons.

In accordance with Federal and Institutional regulations, a Data Safety and Monitoring Board (DSMB) for this study will meet quarterly to review aggregated study outcomes data and adverse events. The DSMB will be composed of three clinical investigators with expertise in working with men/fathers, forensic populations, and IPV victims/child witnesses who are not affiliated with this study. [name] will present these aggregated data on study outcomes and adverse events quarterly in a blinded fashion.

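### Phase II Aim 1 has no therapist term, only a preliminary check with no stated consequence; if therapists are nested in arm and differ, the arm-comparison standard errors are too small

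*Combined protocol and SAP*

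**What the plan says.** Section IV, Analytic Plan, Preliminary Analysis lists as its fifth item a plan to "assess whether there are significant differences in outcomes based on study therapist". Nothing is said about what a significant or a non-significant result would change.

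For Phase II Aim 1 the plan says: "Group differences in changes will be tested in multiple group LGM models". The trajectories are those of individual cases. The Aim 1 text, including its power statement, contains no therapist level, therapist effect, clustered standard error, ICC or number of therapists. The Aim 2 and Aim 3 texts name no therapist term either.

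On who delivers what, the Therapist Training paragraph says: "Master's level clinicians will be trained to deliver the study interventions". For one treatment, "She will meet weekly with F4C therapists for supervision"; for the other, "BIP clinicians will meet weekly with" a different supervisor. The Treatment Fidelity paragraph has feedback given "in their respective supervision sessions with study therapists", and Roles and Responsibilities again assigns supervision by treatment. No sentence says that a clinician delivers only one treatment.

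On masking, the lead analyst or "another team member masked to participant treatment group will carry out all statistical analyses".

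**The concern.** Each father is treated individually by one therapist over 18 weeks, so fathers who share a therapist may have correlated outcomes. If each therapist works in one arm only, differences between therapists add to the variance of the difference between arms. A model that treats fathers as independent leaves that variance out: its intervals are too narrow, and it rejects too often when there is no treatment effect. Aim 1 is the efficacy comparison, so this is where the error would matter most.

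A preliminary significance check does not settle the matter. With few therapists it can easily miss an ICC large enough to distort the comparison. Because no consequence is stated, the response to it is also left to discretion.

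**Working it through.** **Plan's own figure.** The plan gives no figure for therapist clustering. Its Aim 1 power of .91 at d = 0.12 does not come out of a simple two-sample calculation with 140 per arm (0.17, two-sided 5%). That is a separate issue, so 0.91 is not the benchmark here. The unclustered two-sample value is: 140 per arm detects d = 0.34 with 80% power.

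**Inputs from the document.** 140 per arm (Aim 1 Power); 98 per arm, half of the 196 complete cases expected in Section V, How was this estimate derived?; four assessments (baseline, post-treatment, 6 and 12 months later).

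**Assumed inputs.** k = 4, 6 or 10 therapists per arm, nested in arm, with equal caseloads; ICC 0.01 to 0.05; two-sided 5% test.

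**1. Single endpoint, therapist ignored.** DEFF = 1 + (n/k − 1) × ICC, and actual error = 2 × [1 − Φ(1.96/√DEFF)]. For example, with n = 140, k = 6 and ICC 0.02: DEFF = 1 + (23.3 − 1) × 0.02 = 1.45, √1.45 = 1.20, error 10.3%. Results for 140 per arm:

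| ICC | k = 4 | k = 6 | k = 10 |
|---|---|---|---|
| 0.01 | 9.0% | 7.6% | 6.5% |
| 0.02 | 13.0% | 10.3% | 8.1% |
| 0.05 | 23.3% | 17.8% | 12.7% |

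With 98 per arm the range is 6.0% to 18.4%. Simulation (20,000 trials per cell) agrees, and at ICC 0 the error is about 5%.

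**2. Slope comparison, closer to the planned model.** Waves are at 0, 18/52 = 0.346, 0.846 and 1.346 years, so the sum of squared deviations of time is 1.037. With a true-slope SD of 1 and residual SD of 0.5, 1.0 or 1.5, slope reliability is 1/(1 + SD²/1.037) = 0.81, 0.51 or 0.32. The ICC on true slopes is multiplied by this reliability in the DEFF formula. Actual error over the same k and ICC:

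| Reliability | 140 per arm | 98 per arm |
|---|---|---|
| 0.81 | 6.2%–20.3% | 5.8%–16.0% |
| 0.51 | 5.8%–15.1% | 5.5%–12.1% |
| 0.32 | 5.5%–11.4% | 5.3%–9.4% |

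This proxy lets therapist differences act on a linear slope through 12 months after treatment, which is itself an assumption. The multiple-group LGM was not simulated.

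**3. The check used as a gate.** Here the check is a pooled F test of therapist within arm, and therapist enters the arm comparison only when that test is significant. With 140 per arm:

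| ICC | Power of check (k = 4/6/10) | Error after gating (k = 4/6/10) |
|---|---|---|
| 0.01 | 0.16 / 0.13 / 0.11 | 7.8% / 6.5% / 5.9% |
| 0.02 | 0.29 / 0.25 / 0.20 | 9.9% / 7.5% / 6.6% |
| 0.05 | 0.61 / 0.60 / 0.52 | 10.2% / 8.2% / 7.5% |

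With 98 per arm, power is 0.09 to 0.21 at ICC 0.01–0.02 and 0.36 to 0.47 at ICC 0.05, and the gated error is 5.7% to 10.3%. After a non-significant check, the unadjusted test is as inflated as with no check (24.1% against 23.8% at ICC 0.05, k = 4, 140 per arm).

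**4. Clinicians deliver both treatments.** With 8 to 20 clinicians, each delivering both treatments equally, and a general-ability ICC of 0.02 to 0.05, error is 4.4% to 5.0% without therapist-by-treatment variance. It is 5.2% to 9.0% if that variance is 1% to 2% of the total.

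**5. Therapist-level analysis.** A comparison of therapist means with 2(k − 1) degrees of freedom holds 4.6% to 5.4% in every cell, including ICC 0. With SE = √(2 × DEFF/n) and the noncentral t, detectable d at ICC 0.01–0.05 is 0.38 to 0.66 for 140 per arm, against 0.34 unclustered. For 98 per arm it is 0.44 to 0.71, against 0.40.

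**The case against.** The strongest reply is that nesting is inferred. Separate supervision by treatment is compatible with one clinician attending both, and training clinicians to deliver the study interventions does not bar it. Some of the text also covers Phase I: the training paragraph names the group-format BIP arm, and the monitoring plan's protocol summary names only the Yale clinic although Phase II also uses UConn. This stands, and it is why the point is conditional.

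The size rests on assumed therapist numbers and ICC. This also stands: within the slope proxy alone the consequence runs from negligible to serious. The 23% is a single-endpoint figure at the worst corner of the grid, not the planned analysis.

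The check is not uniformly weak. Its power reaches 0.61 at ICC 0.05 with 4 therapists per arm, where inflation is greatest. Even there, gating leaves 10.2%.

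The Analytic Plan also refers to a Statistical Analysis section and a Statistical Design and Power section that are not in the document reviewed. A therapist provision there cannot be excluded; if one exists, citing it may be enough.

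A reader might infer that the plan ignores therapists, or that this trial's false-positive rate will be about 20%. The documents support neither. A therapist check is planned, and neither the allocation of therapists nor the ICC is given.

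**Conclusion.** The point holds in conditional form. In the text available, the Aim 1 model has no therapist term, and the only safeguard is a significance check with no stated consequence. The standard errors of the arm comparison are too small if three conditions hold together: therapists nested in arm, ICC above zero, and therapist omitted from the final model. If the ICC is zero, or if clinicians deliver both treatments without therapist-by-treatment variance, there is no inflation.

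The sizes are illustrations over assumed ranges, not estimates for this trial. Confidence is medium, because nesting is suggested and not stated. Whichever allocation applies, the plan should say what it is and what the check leads to.

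**What to change.** - State how many therapists each arm has and whether any clinician delivers both treatments.
- If therapists are nested, account for therapist within arm in the Aim 1 comparisons whatever the check shows, with degrees of freedom based on the number of therapists. Pre-specify a therapist-level summary analysis in case the two-level growth model cannot be estimated. Use coded therapist identifiers so that the analyst stays masked.
- If clinicians cross arms, address therapist-by-treatment variance instead.
- Restate power over a range of ICC and therapist numbers. Acknowledge that, under nesting, differences in ability between the two therapist pools stay confounded with treatment whatever variance correction is used.

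**Cost.** This takes SAP wording and a more complex model. No new data appear to be needed, since therapists already file weekly session reports. Intervals widen, stated power becomes less favourable, and the two-level model may not converge. Even at ICC 0, the lost degrees of freedom raise detectable d from 0.34 to between 0.35 (10 therapists per arm) and 0.40 (4 per arm) with 140 fathers per arm. With 4 therapists per arm a random-intercept test is conservative: actual error 1.1% at ICC 0 and 4.5% at ICC 0.05.

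**Separately, for precision.** Adjust the Phase II arm comparisons for the father-level stratification variables actually used. The Stratified Randomization text lists residence with the target child, protective order with the coparent and substance use, and an item may be missing from that list. Add site only after weighing its cost: if each therapist works at one site, it uses a therapist-level degree of freedom. With 4 therapists per arm, 140 fathers per arm, ICC 0.01 and an assumed R-squared of 0.05, detectable d would go from 0.466 to 0.474, a small loss.

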Child Mental Health. Symptom dimensions will be derived from father and mother reports on surveys with established reliability, validity, and developmental sensitivity. For data reduction purposes, continuous latent constructs will be identified via measurement models and secondorder factor models conducted in Mplus using standard fit criteria. If necessary, we will use other methods to reduce these data, e.g., latent constructs formed by principal components analysis. The TSCYC and TSCC includes 8 subscales assessing trauma symptoms and more common childhood symptoms and are used for children aged 3 to 17. For infants and toddlers, we will have parents complete the Brief Infant Toddler Social Emotional Assessment (ITSEA) Stratified Randomization. To increase the likelihood treatment groups are balanced on important variables (i.e., , residence with target child, protective order with coparent, substance use) participants will be assigned to treatment through stratified randomization. Following randomization, fathers will be assigned to either 18 sessions (once per week) of Fathers for Change or18 sessions of Duluth Batterer Intervention delivered in an individual format. We anticipate 140 participants in each treatment group. Research assistants managing the data [name] will be blind to treatment condition assignment during analysis. Participants will be recorded as receiving either "treatment 1", or "treatment 2". The research assistants and [name] will not be aware which treatment protocol "treatment 1" or "treatment 2" correspond to until analyses are complete.

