# Phase II:

The target sample is 280 father-coparent dyads and their 9 months to 11 year-old children recruited from CPS-involved families referred to the Parent and Family Development Program (PFDP) at Yale or the UCONN Health Center Outpatient Psychiatry Clinic. Participants will be randomized to either F4C (n = 140) or BIP (n = 140) following a baseline assessment. Half of F4C and BIP families will be treated at Yale and half at UConn Health. Yale will serve families in

Greater New Haven region, while UConn Health will serve families in the Greater Hartford region. The two sites are approximately a 45-minute drive apart.

5. **Describe** how access to the population will be gained in the study.

Fathers referred to the Parent and Family Development Program or UCONN Health Center by the CT Department of Children and Families (DCF) or the community due to IPV or child maltreatment risk will be provided information about the study and asked to complete an initial brief screening if they are interested in participation. He will be told that his screening questionnaire (which will include demographic matching information such as age, ethnicity, city of residence, income, employment history, SA history etc.) will be reviewed and he will be contacted to set up further assessment sessions if he is found eligible by the PI based on our study's requirements. This will provide the opportunity for contact with the mother to conduct phone screening with her related to IPV and her willingness for their shared child to participate. Female co-parent and intimate partner contact information will be provided on the referral from DCF or community referral source so that fathers are not providing this information, and this will limit the possibility of coercion.

6. **Participant classification:** Check off all classifications of participants that will be specifically recruited for enrollment in the research project. Will participants who may require additional safeguards or other considerations be enrolled in the study? If so, identify the population of participants requiring special safeguards and provide a justification for their involvement.

🛛 Healthy	□Fetal material, placenta, or dead fetus
Prisoners	□Economically disadvantaged persons
🗆 Employees	□Pregnant women and/or fetuses
□ Females of childbearing pote	ential
	
 
Healthy
 
Prisoners
 
Employees
 
Females of childbearing pote
 

Click or tap here to enter text.

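### Phase II allocation is balanced on three baseline factors, but the Aim 1 growth models specify no adjustment for them or for site, so the test as described is conservative and may lose some power

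*Combined protocol and SAP*

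**What the plan says.** The stratified randomization paragraph, which follows the child mental health measures in Section IV.3, names the three balancing factors: "residence with target child, protective order with coparent, substance use) participants will be assigned to treatment through stratified randomization". Site is not among them. The preliminary analysis paragraph of the Analytic Plan gives the method another name and states the one use of the factors: "Although urn randomization procedures will be used to balance distribution of specific characteristics across treatment groups, we will explore between-group differences in urn variables". That sentence goes on to cover other demographics and possible moderators. The same paragraph lists a preliminary check to "assess whether there are significant differences in outcomes based on study therapist".

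For the Aim 1 test, Phase II Hypotheses says "Hypotheses will be evaluated with the broad family of latent (growth) curve models (LGM" and then "Group differences in changes will be tested in multiple group LGM models". It names no covariate: no balancing factor, no site term, no therapist term.

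Section IV.4 sets the size and the sites: "Participants will be randomized to either F4C (n = 140) or BIP (n = 140) following a baseline assessment", and "Half of F4C and BIP families will be treated at Yale and half at UConn Health". It does not say whether allocation is run separately within each site.

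**The concern.** Forced balance on a prognostic factor removes that factor's chance imbalance from the treatment contrast. A model without the factor still counts its variance as noise, so the reported standard error is larger than the true sampling error of the estimate. Confidence intervals are then too wide, the test rejects less often than its nominal level, and power that the balanced design could deliver goes unused.

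The preliminary exploration does not fill the gap. Properly randomised arms differ at baseline only by chance, so comparing them does not show which covariates the model needs. It also leaves the choice of covariates open until data have been seen.

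Stratified and urn randomization are different procedures. How tightly the arms are balanced, and on what, depends on which is used and whether it is run within site.

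**Working it through.** **The plan's own figure.** Phase II Hypotheses states power of 0.91 at d = 0.12 with 140 per group. A two-sample comparison (two-sided, alpha 0.05) gives about 0.17. Repeated-measures formulas come near 0.91 only with inputs the plan does not give; for example, d = 0.12 read as f = 0.06, with 280 fathers, four waves and a within-person correlation of 0.7, gives 0.881. The figure could not be reproduced from the stated inputs. That is a separate matter and does not decide this point, so the effect of adjustment is worked out directly.

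**Inputs**
- Complete cases: Section V, on how the sample size was derived, expects 196 of 280, so 196 / 2 = 98 per arm. Phase II Hypotheses instead says 126 per group after 30% attrition. But 0.70 × 140 = 98, while 126 = 0.70 × 180, the other group size in the same paragraph.
- R², the share of variance in outcome change that the balancing factors explain: not given. Assumed 0.02 to 0.30.
- Alpha 0.05 two-sided and 80% power: assumed. Normal quantiles are 1.960 and 0.842.
- Balance: assumed near-perfect.

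**Formulas.** Let s = √(1 − R²). In outcome SD units, the unadjusted model reports SE = √(2/98) = 0.1429. Under balance the true SE of the estimate is s × 0.1429, whether or not the model adjusts.
- Type I error, unadjusted = 2 × [1 − Φ(1.960 / s)]
- Detectable d, unadjusted = (1.960 + 0.842 s) × 0.1429
- Detectable d, adjusted = (1.960 + 0.842) × s × 0.1429
- Gain in effective sample size = (unadjusted d / adjusted d)² − 1

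For R² = 0.10, s = 0.949. Unadjusted: (1.960 + 0.799) × 0.1429 = 0.394. Adjusted: 2.802 × 0.949 × 0.1429 = 0.380. Gain: about 8%.

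| R² | s | Type I error, unadjusted | d, unadjusted | d, adjusted | Gain |
|---|---|---|---|---|---|
| 0.02 | 0.990 | 4.8% | 0.399 | 0.396 | 1% |
| 0.05 | 0.975 | 4.4% | 0.397 | 0.390 | 4% |
| 0.10 | 0.949 | 3.9% | 0.394 | 0.380 | 8% |
| 0.20 | 0.894 | 2.8% | 0.388 | 0.358 | 17% |
| 0.30 | 0.837 | 1.9% | 0.381 | 0.335 | 29% |

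The percentage gain does not depend on the number per arm, so it is the same at 126. Adjustment lowers the reported SE by 1 − s, which is 1% at R² = 0.02, 2.5% at 0.05 and 16% at 0.30.

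**Check by simulation.** 4,000 trials of 280 families were simulated with 16 strata (site and three binary factors), permuted blocks of 4, and a linear model for one change score per family. Unadjusted type I error was 0.053, 0.048, 0.038, 0.026 and 0.017 at R² of 0, 0.05, 0.10, 0.20 and 0.30. Adjusted, it stayed between 0.041 and 0.055. At R² = 0.20 the unadjusted model reported an SE of 0.119 against a true 0.106; the adjusted model reported 0.107 against 0.105. The simulation replaces the full growth model with a change score, the urn with blocks, and assumes stratification by site.

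**The case against.** The strongest reply is that the plan is silent rather than wrong. Latent growth models accept covariates, nothing says the factors will be left out, and the plan points to a statistical analysis section and a statistical design and power section that are not in the text available here. This stands: the documents support saying that adjustment is not specified, not that it is ruled out. If those sections list the covariates, only the conflict over the allocation method remains.

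Second, the size is assumed. The Aim 1 test concerns change. A factor such as residence with the child may mainly predict level, which the growth intercept absorbs. This also stands, so the range has to start near zero. Against it, the plan itself calls the balancing variables important, and its account of the weekly timeline follow-back ties relationship violence to substance use.

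Third, adjustment in a multiple-group model is not automatic. Four covariates on two growth factors in two arms make 4 × 2 × 2 = 16 paths. With uncentred covariates and free paths, the between-arm contrast refers to families with every covariate at zero. This stands and shapes the fix.

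A reader might infer several stronger things that the documents do not support:
- *False positives are inflated.* The error runs the other way: type I error falls below 5%.
- *The treatment estimate itself loses precision.* Balance has already secured it; the true SE is almost the same with or without adjustment. What is lost is reported precision, and power with it.
- *Adjustment is worth 11% to 43% more fathers,* from 1 / (1 − R²) − 1 at R² of 0.10 and 0.30. That formula compares adjustment with an unbalanced design. Under forced balance the gain is 8% to 29%.
- *Site is a stratifier.* Half the families at each site is a recruitment plan. Unless allocation is run within site, the standard-error argument does not reach it and site is an ordinary prognostic covariate.

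**Conclusion.** The point holds as a gap in prespecification with a conservative consequence. Validity is not threatened. If the Aim 1 models are fitted as described, the standard errors will be too wide whenever the balancing factors predict change. The loss runs from negligible (R² of 0.05 or less) to the equivalent of about 29% of the effective sample size (R² of 0.30). These sizes rest on an assumed R², near-perfect balance and a two-sample approximation to the growth model; looser balance under an urn would make the mismatch smaller. The correction is worth making before analysis because it is cheap, closes a choice otherwise left until after data are seen, and resolves which allocation method was used.

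**What to change.** - Name one allocation method, and say whether it is run within site.
- In the Aim 1 text, prespecify the three balancing factors as covariates on the intercept and growth factors. Centre them and constrain their paths to be equal across arms, or enter treatment as a covariate in a single-group growth model. Either keeps the between-arm growth contrast interpretable.
- Add site as a prognostic covariate, or as a stratifier if allocation is within site. Reconcile the site figures at the same time: half of 280 is 140 fathers, but Targeted Enrollment gives 180 at Yale, and the protocol summary in the data and safety monitoring plan names only the Yale clinic.
- Carry the same covariates into the Aim 3 mediation models.
- Report the comparison of urn variables descriptively, and state that it will not be used to choose covariates.

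The cost is SAP wording and a few model parameters: with equal paths, 4 covariates × 2 growth factors = 8. No new data are needed. The balancing factors must be known before allocation, and site is known for every family.
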